Fred Hutchinson Cancer Research Center
Clinical Study Protocol [FHCRC 9266]

CLINICAL STUDY PROTOCOL

FHCRC # 9266

FRED HUTCHINSON CANCER RESEARCH CENTER
UNIVERSITY OF WASHINGTON SCHOOL OF MEDICINE
 Millennium Study Number: X16064

Alternating the Administration of Ixazomib and Lenalidomide as Maintenance Therapy after Autologous Transplant for Treating Multiple Myeloma

Indication: Maintenance therapy after autologous Tx for Multiple Myeloma

Phase: **II**

Protocol History

Original	02 July 2015
Previous	30 October 2015
Previous	28 December 2015
Previous	03 July 2018
Current	16 September 2019

Investigator and Study Center:

Principal Investigator

[name], PhD Member, FHCRC, Professor of
 Medicine, UW

FHCRC
 [name]
 [name]
 [name]
 [contact] phone

FHCRC Emergency (24 hours) [contact]; **[contact]

This is an investigator-initiated study. The principal investigator [name] [name] (who may also be referred to as the sponsor-investigator), is conducting the study and acting as the sponsor. Therefore, the legal/ethical obligations of the principal investigator include both those of a sponsor and those of an investigator.

**Fred Hutchinson Cancer Research Center
Clinical Study Protocol [FHCRC 9266]**

PROTOCOL SUMMARY

Fred Hutchinson Cancer Research Center
Clinical Study Protocol [FHCRC 9266]

Study Title: Alternating the Administration of Ixazomib and Lenalidomide as Maintenance Therapy after Autologous Transplant for Treating Multiple Myeloma

Phase: II

Number of Patients: 30

Study Objectives

Primary

- Evaluate the toxicity of the use of ixazomib and lenalidomide as maintenance therapy after autologous transplant

Secondary

- Evaluate the ability to deliver the planned therapy
- Assess initial response to therapy
- Evaluate the median time to disease progression
- Assess overall survival

Overview of Study Design:

Hypothesis of this phase II study is that ixazomib and lenalidomide as maintenance therapy after autologous PBSC transplant for Multiple Myeloma will be safe and tolerable and prolong the time to disease progression post transplant. The treatment regimen is alternating ixazomib with lenalidomide every two months until disease progression, intolerable toxicity or maximum of 24 months of therapy. The dose of ixazomib is 4.0 mg po on days 1, 8 and 15 per each 28-day cycle given for two consecutive months, followed by then lenalidomide 10 mg po daily for two consecutive months, then ixazomib for two months etc. Dose reduction for toxicity will be incorporated. If >30 days off initially planned next cycle of therapy, then patient will be taken off study. Toxicity will be graded per CTCAE version 4.0. The first four months of therapy will be used as the time period to evaluate end point of toxicity for stopping rules. Toxicity that meets stopping rules will be determined based on the number of patients that are withdrawn from study for significant toxicity (grade IV, non-hematological, non-metabolic, non-peripheral neuropathy) and the number of patients who stop therapy for toxicity and are withdrawn from study as they could not recover adequately and resume therapy by 30 days from the initial stopping of the study drugs. We shall consider the withdrawal rate to be excessive, and hence the therapy to be too toxic, if the true withdrawal rate from the study exceeds 15% in the first four months. An interim analysis at 15 treated patients will be conducted. If > 50% of patients are unable to receive > 50% of planned therapy in first 12 months of treatment, the study will be terminated due to lack of feasibility. Another endpoint is time to disease progression. Patients will be followed for initial response and for progression of disease, response criteria will be determined by International Myeloma working group criteria. In patients with chemo-refractory disease at the time of ASCT, the therapy will be felt to be promising if median time to progression is >9 months. If chemo-sensitive disease at time of ASCT, the therapy will be felt to be promising if median time to progression is >41 months based on CALGB 10014 lenalidomide maintenance study post ASCT. Cytogenetic information will be collected and initial response rates and outcome will be descriptively reported. Patients will be followed for overall survival. The incidence of secondary cancers will also be collected. If this study regimen is deemed to be potentially efficacious and is not regarded as too toxic per stopping rules outlined above and observed EFS rate are consistent with rates that match or exceed historical benchmarks, then a phase III trial to show efficacy rate of this regimen over single agent therapy will be designed.

Study Population:

Adult Autologous Multiple Myeloma Transplant patients

Duration of Study:

Five years (2-3 years to enroll patients on study)

Fred Hutchinson Cancer Research Center
Clinical Study Protocol [FHCRC 9266]

SCHEDULE OF EVENTS

Study Flow Chart

(Each cycle is 28 days) Cycle			1-4 cycles			5-24 cycles			
Day	Screening (Baseline within 30 days)	Predose Day (within 3 days) to Day 1 of Cycle 1-4	Day 8 (+/- 3 days) Week one	Day 15 and 22 (+/- 3 days) Weeks 2 and 3	Predose Day (within 3 days) to Day 1 of Cycle 5-24	Day 8 (+/- 3 day) Week one	Day 15 (+/- 3 days) Week 2	End of Study (Labs within 7 days and other tests within month after last dose of drug)	Survival Follow-up
Phase	Screening	Pretreatment	Treatment	Treatment		Treatment	Treatment	Post- Treatment	Post- Treatment
Study Procedures									
Obtain study informed consent		X							
Demographics		X							
Review Inclusion/Exclusion criteria		X							
Review/collect prior medications		X							
Collect medical history		X							
Enroll Revlimid REMS TM program pre cycle 3			X						
Safety Labs/ Measurements									
Collect serum β -hCG pregnancy test ^b	X	X ^b							
Collect CBC	X	X	X	X	X	X	X	X	X
Collect blood chemistry	X	X	X	X	X	X		X	X
Collect PT/INR & aPTT ^a	X								
Collect urinalysis (complete)	X								
Collect 24-hour urine creatinine clearance	X								

Fred Hutchinson Cancer Research Center
Clinical Study Protocol [FHCRC 9266]

Cycle	-----	1-4			5-24			-----
Day	Screening (Baseline) Within 30 days prior to first dose	Predose Day (within 3 days Day 1 of Cycle 1-4)	Day X (+/- 3 days) Week one	Day X Cycle 1-24	Pre dose within 3 days	Day X (+/- 3 days) Week one	Day X (+/- 3 days) Week 2	End of Study (within month after last dose of drug) Survival Follow-up
Phase	Screening	Pretreatment	Treatment	Treatment	Treatment	Treatment		Post-treatment Post-Treatment
Review concomitant medications	X	X			X			
Review adverse experiences		X			X			X
ECOG Performance Status	X	X			X			X X
Perform physical examination and collect vital signs (including height at screening and weight at all visits)	X	X			X			X X
Efficacy Measurements								
MRI Bone Marrow and osseous survey								X X (yearly)
BM aspirate and biopsy unilateral for pathology, flow, cytogenetics and myeloma FISH panel	X							X X (yearly)
Serum free light or SPEP with IF	X			X (every 3 months)				X X (every 3 months)

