6.2.1 Ixazomib Administration

All protocol-specific criteria for administration of study drug must be met and documented before drug administration. Study drug will be administered or dispensed only to eligible patients under the supervision of the investigator or identified subinvestigator(s). Patients should be monitored for toxicity, as necessary, and doses of ixazomib should be modified as needed to accommodate patient tolerance to treatment; this may include symptomatic treatment, dose interruptions, and adjustments of ixazomib dose (see Section 9.3).

Capsules of ixazomib will also be referred to as study drug. Study drug will be supplied by Millennium as capsules of 2.3-, 3.0- and 4.0 mg ixazomib. This is dependent on available ixazomib formulation.

The prescribed administration of ixazomib doses in this study is 4 mg ixazomib on days 1, 8 and 15 of each 28 day cycle for two cycles in a row followed then by lenalidomide therapy for two 28 day cycles for a total of 24 months of therapy.

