6.4 Dose-Modification Guidelines

6.4.1 Recommended Ixazomib Criteria for Beginning or Delaying a Subsequent Treatment Cycle & Dose Modifications for Treatment Associated Toxicity

Treatment with ixazomib will use a cycle length of 28 days. For a new cycle of treatment to begin, the patient must meet the following criteria:

- ANC must be $\geq 1,000/\text{mm}^3$.
- Platelet count must be $\geq 75,000/\text{mm}^3$.
- All other nonhematologic toxicity (except for alopecia) and peripheral neuropathy must have resolved to \leq Grade 1 or to the patient's baseline condition.

If the patient fails to meet the above-cited criteria for initiation of the next cycle of treatment, dosing should be delayed for 1 week. At the end of that time, the patient should be re-evaluated to determine whether the criteria have been met. If the patient continues to fail to meet the above-cited criteria, delay therapy and continue to reevaluate. The maximum delay before treatment should be discontinued will be 30 days or at the discretion of the Principal Investigator.

For dosing recommendations upon recovery, refer to Table 6-1, Table 6-2, and Table 6-3.

**Fred Hutchinson Cancer Research Center
Clinical Study Protocol [FHCRC 9266]**

Table 6-1 Ixazomib Dose Adjustments

Dose Level	Dose (mg)
Starting Dose	4.0 mg
-1	3.0 mg
-2	2.3 mg
-3	Discontinue

Dosing adjustments for hematologic toxicity are outlined in Table 6-2.

Table 6-2 Ixazomib Dose Adjustments for Toxicities

Criteria	Action
Within-Cycle Dose Modifications	
• If platelet count $\leq 30 \times 10^9/L$ or ANC $\leq 0.50 \times 10^9/L$ on a ixazomib dosing day (other than Day 1)	
• Ixazomib dose should be withheld.• Complete blood count (CBC) with differential should be repeated at least every other day until the ANC and/or platelet counts have exceeded the prespecified values (see Section 6.4.1) on at least 2 occasions.• Upon recovery, ixazomib may be reinitiated with 1 dose level reduction.
Dose Modifications for Subsequent Treatment Cycles	

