6.13 Storage, Handling, and Accountability

Upon receipt at the investigative site, ixazomib should remain in the blister and carton provided until use or until drug is dispensed. The container should be stored at the investigative site according to storage conditions detailed in the Investigator's Brochure. Ensure that the drug is used before the retest expiry date provided by Millennium. Expiry extensions will be communicated accordingly with updated documentation to support the extended shelf life.

In countries where local regulations permit, ixazomib capsules dispensed to the patient for take-home dosing should remain in the blister packaging and refrigerated as noted above until the point of use. The investigative site is responsible for providing the medication to the patient in the correct daily dose configurations. Comprehensive instructions should be provided to the patient in order to ensure compliance with dosing procedures. Patients who are receiving take-home medication

**Fred Hutchinson Cancer Research Center
Clinical Study Protocol [FHCRC 9266]**

should be given only 1 cycle of medication at a time. Patients should be instructed to store the medication according to storage conditions detailed in the Investigator's Brochure for the duration of each cycle. Patients should be instructed to return their empty blister packs to the investigative site, rather than discarding them. Reconciliation will occur accordingly when the patient returns for their next cycle of take-home medication. Any extreme in temperature should be reported as an excursion and should be dealt with on a case-by-case basis.

Because ixazomib is an investigational agent, it should be handled with due care. Patients should be instructed not to chew, break, or open capsules. In case of contact with broken capsules, raising dust should be avoided during the clean-up operation. The product may be harmful by inhalation, ingestion, or skin absorption. Gloves and protective clothing should be worn during cleanup and return of broken capsules and powder to minimize skin contact.

The area should be ventilated and the site washed with soap and water after material pick-up is complete. The material should be disposed of as hazardous medical waste in compliance with federal, state, and local regulations.

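### The flow-chart window lets the Day 8 and Day 15 CBC be drawn after the ixazomib dose that Table 6-2 may require to be withheld, so the schedule does not ensure that the hold rule can operate.

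*Combined protocol and SAP*

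**What the plan says.** The Study Flow Chart marks a CBC in every column. For cycles 1-4 the mid-cycle columns are "Day 8 (+/- 3 days) Week one" and "Day 15 and 22 (+/- 3 days) Weeks 2 and 3". For cycles 5-24 they are "Day 8 (+/- 3 day) Week one" and "Day 15 (+/- 3 days) Week 2". The draw at the start of a cycle is framed differently, as "Predose Day (within 3 days) to Day 1 of Cycle 1-4", so it may only precede the dose.

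Section 6.2.1 prescribes "4 mg ixazomib on days 1, 8 and 15 of each 28 day cycle" and gives no dosing window. It also states in general terms that the protocol's criteria for giving study drug have to be met and documented first.

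Table 6-2 (Section 6.4.1) has a within-cycle rule. If platelets are at or below 30 x 10^9/L, or ANC is at or below 0.50 x 10^9/L, "on a ixazomib dosing day (other than Day 1", that dose is withheld. The dosing days other than Day 1 are Days 8 and 15.

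On supply, Section 6.13 says that patients with take-home medication "should be given only 1 cycle of medication at a time". The flow chart marks ixazomib dispensing only in the predose columns.

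**The concern.** A rule that withholds a dose on a blood count needs the count in hand before the dose is taken. The Day 1 draw is set up that way; the Day 8 and Day 15 draws are not. A site could follow the flow chart exactly, draw on Day 11, and find that a dose already taken on Day 8 met the condition for withholding. No dispensing step intervenes for take-home patients, because they already hold the cycle's capsules.

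Two things are at stake. The first is patient safety: Section 6.10 acknowledges that thrombocytopenia and neutropenia may be severe. The second is interpretation. The Protocol Summary counts toward the toxicity stopping rule those patients who stop for toxicity and cannot resume within 30 days, and Section 7.1.8 bases feasibility on the share of planned therapy delivered. If some doses are given that the rule would have withheld, later delays and withdrawals could partly reflect draw timing rather than the regimen. The documents give no means of estimating the size of that effect.

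**Working it through.** The plan gives no figure of its own on this point, so there is nothing to reproduce. The check is day arithmetic on the stated windows.

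**Inputs**
- CBC windows: Day 8 +/- 3 and Day 15 +/- 3, in cycles 1-4 and 5-24 (Study Flow Chart).
- Cycle-start CBC: within 3 days before, up to Day 1 (Study Flow Chart).
- Ixazomib doses: Days 1, 8 and 15 (Section 6.2.1).
- Ixazomib cycles: 1-2, 5-6, 9-10, 13-14, 17-18 and 21-22 (drug-dispensing row of the flow chart).
- Hold rule: applies on dosing days other than Day 1 (Table 6-2).

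**Step 1: permitted draw days against the dose day**
- Day 8 window: 8 - 3 = Day 5 to 8 + 3 = Day 11. Days 9, 10 and 11 fall after the dose.
- Day 15 window: 15 - 3 = Day 12 to 15 + 3 = Day 18. Days 16, 17 and 18 fall after the dose.
- Draws on Days 5-8 or 12-15 also comply. These can precede the dose; a same-day draw does so only if the result is seen first.

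**Step 2: age of the latest scheduled count when the draw is late**
- At the Day 8 dose, the latest scheduled count is the cycle-start sample. If drawn on Day 1, it is 8 - 1 = 7 days old. If drawn 3 days earlier, it is 7 + 3 = 10 days old.
- At the Day 15 dose, the latest scheduled count is the Day 8 sample, drawn between Days 5 and 11. It is 15 - 11 = 4 to 15 - 5 = 10 days old.

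**Step 3: doses exposed**
- Ixazomib cycles: 6 pairs x 2 = 12.
- Planned ixazomib doses in a full course: 12 x 3 = 36.
- Doses subject to the within-cycle rule: 12 x 2 = 24 of 36.
- In cycles 1-2, which lie within the four-month toxicity period: 2 x 2 = 4 of 6.

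**Step 4: does any other text close the gap?**
- Section 6.2.1's general sentence sets no CBC timing.
- Section 6.10 refers blood-count monitoring back to the protocol schedule, with extra testing according to standard practice. It adds no requirement for a count before the dose.
- Section 6.6 restricts platelet transfusion in the 3 days before a dose and refers to the within-cycle modifications. This suggests that the authors expected a count before the dose, but it does not schedule one.
- No passage says that the dose moves with the visit.

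**The case against.** The strongest reply is Section 6.2.1. The count limit in Table 6-2 reads naturally as one of the criteria to be met and documented before administration, so a site that follows the whole protocol would not give the Day 8 dose and look at the count on Day 11. This has force: the gap opens only for a site that works from the flow chart alone. But if Section 6.2.1 does require a count before the dose, the flow chart permits draws that Section 6.2.1 does not, and the two still need aligning.

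A reader might infer that the schedule and Table 6-2 contradict each other outright. The documents do not support that. Step 1 shows draw days that satisfy both. The window is permissive, not incompatible.

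It can also be said that the 3 days are a visit window and that dose and draw move together. Section 6.2 does allow a missed dose to be taken late if the next is at least 72 hours away. A Day 8 dose taken on Day 11 leaves (15 - 11) x 24 = 96 hours, so it would qualify. That sentence is written for forgotten doses, however. It does not tell anyone to wait for a count, and Section 6.2.1 names fixed days.

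Finally, the hold is not the only safeguard. Cycle-start count criteria, additional testing, growth factors and transfusion are all provided for, and careful clinicians may check the count first in any case. All of that stands. It limits the likely harm but does not put a count before the dose.

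**Conclusion.** The point holds in a limited form. A schedule-compliant CBC can come up to 3 days after the dose to which Table 6-2's hold applies, so the schedule does not ensure that the hold can work. Up to 24 of 36 planned ixazomib doses per full course are exposed, 4 of them in cycles 1-2. Lenalidomide cycles are outside the point.

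This rests on two readings. One is that the Day 8 and Day 15 CBCs are the counts intended for the hold, which is inferred from Table 6-2's reference to dosing days because the flow chart does not say so. The other is that doses are taken on their nominal days.

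Two stronger inferences are not supported. Three of the seven permitted days (3/7 = 43%) fall after the dose, but that is a share of calendar days and not a probability that a draw will be late; that probability is unknown. Nor do the pooled rates in Table 1-2 (thrombocytopenia 33% overall and 41% with single-agent ixazomib, neutropenia 21% overall) size the problem. They carry no grade restriction, are not tied to Day 8 or Day 15, and pool different doses and schedules. Section 1.10.1 does mention reduced marrow reserve early after transplant, but as a reason for the dosing schedule and not for the hold.

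**What to change.** The sponsor should reconcile three places for the ixazomib cycles: the CBC windows in the Study Flow Chart, the general pre-administration sentence in Section 6.2.1, and the within-cycle rule in Table 6-2. After that, the scheduled count should be able to serve the hold already written. The text should also settle what counts as a value on a dosing day, since a Day 5 draw precedes the Day 8 dose but is not a dosing-day count. The wording is for the sponsor to decide; no count limit, dose or action is proposed here.

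The change can be made as a flow-chart footnote with a matching cross-reference and need not add draws. Its cost is less scheduling flexibility at two draws per ixazomib cycle.

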Abbreviation	Term
AE	adverse event
ALP	alkaline phosphatase
ALT	alanine aminotransferase
ANC	absolute neutrophil count
aPTT	activated partial thromboplastin time
ASCO	American Society of Clinical Oncology
ASCT	Autologous Peripheral Blood Stem Cell Transplant
AST	aspartate aminotransferase
AUC	area under the plasma concentration versus time curve
AUC _{24 hr}	area under the plasma concentration versus time curve from zero to 24 hours
AUC _{inf}	area under the plasma concentration versus time curve from zero to infinity
AUC _τ	area under the plasma concentration versus time curve from zero to next dose
βhCG	beta-human chorionic gonadotropin
BID	bis in die; twice a day
BM	bone marrow
BSA	body surface area
BUN	blood urea nitrogen
BZD	Benzodiazepines
CBC	complete blood count
CFR	Code of Federal Regulations
CL _P	plasma clearance
CL _{Total}	total clearance
C _{max}	single-dose maximum (peak) concentration
CNS	central nervous system

**Fred Hutchinson Cancer Research Center
Clinical Study Protocol [FHCRC 9266]**

Abbreviation	Term
CO ₂	carbon dioxide
CR	complete remission
C _{trough}	single-dose end of dosing interval (trough) concentration
CV	coefficient of variation
CYP	cytochrome P ₄₅₀
DDI	drug-drug interaction
DLT	dose-limiting toxicity
DME	drug metabolizing enzymes
DNA	deoxyribonucleic acid
ECG	Electrocardiogram
ECOG	Eastern Cooperative Oncology Group
ELISA	enzyme-linked immunosorbent assay
EOS	End of Study (visit)
EOT	End of Treatment (visit)
FDA	United States Food and Drug Administration
GCP	Good Clinical Practice
G-CSF	granulocyte colony stimulating factor
GGT	gamma glutamyl transferase
GI	Gastrointestinal
GLP	Good Laboratory Practices
GMP	Good Manufacturing Practice
Hb	Hemoglobin
Hct	Hematocrit
HIV	human immunodeficiency virus
IB	Investigator's Brochure
IC ₅₀	concentration producing 50% inhibition
ICF	informed consent form
ICH	International Conference on Harmonisation
IEC	independent ethics committee
IRB	institutional review board
ITT	intent-to-treat

**Fred Hutchinson Cancer Research Center
Clinical Study Protocol [FHCRC 9266]**

Abbreviation	Term
IV	intravenous; intravenously
K _i	inhibition constant
KPS	Karnofsky Performance Status
LDH	lactate dehydrogenase
LFT	liver function test(s)
MedDRA	Medical Dictionary for Regulatory Activities
Millennium	Millennium Pharmaceuticals, Inc., and its affiliates
MRI	magnetic resonance imaging
MRU	medical resource utilization
MTD	maximum tolerated dose
MUGA	multiple gated acquisition (scan)
NCCN	National Comprehensive Cancer Network
NCI	National Cancer Institute
NCI CTCAE	National Cancer Institute Common Terminology Criteria for Adverse Events
NPO	nothing by mouth
NYHA	New York Heart Association
PBMC	peripheral blood mononuclear cell
PCR	polymerase chain reaction
PD	progressive disease (disease progression)
Pgp	P-glycoprotein
PK	pharmacokinetic(s)
PO	per os ; by mouth (orally)
PR	partial response
PRO	patient-reported outcome
QD	quaque die ; each day; once daily
QOD	quaque altera die ; every other day
RBC	red blood cell
SAE	serious adverse event
SD	stable disease
SmPC	Summary of Product Characteristics
t _{1/2}	terminal disposition half-life

**Fred Hutchinson Cancer Research Center
Clinical Study Protocol [FHCRC 9266]**

Abbreviation	Term
TGI	tumor growth inhibition
T _{max}	single-dose time to reach maximum (peak) concentration
ULN	upper limit of the normal range
US	United States
V _z	volume of distribution in the terminal phase
VGPR	Very good partial response
WBC	white blood cell
WHO	World Health Organization

